Title Page

A Comparison of Two Different Anesthetic Application (Sedation / Analgesia & LMA) on Anxiety Level and Patient Satisfaction in Patients with in Vitro Fertilization: Prospective Randomized Clinical Trial

***[name]**, Asst. [name] of Anesthesiology and Reanimation, Inonu University Faculty of Medicine, Malatya, Turkey.

[name], Asst. [name] of Anesthesiology and Reanimation, Inonu University Faculty of Medicine, Malatya, Turkey.

[name], [name]. Division of Reproductive Endocrinology, Department of Obstetrics and Gynecology, Inonu University Faculty of Medicine, Malatya, Turkey.

[name]. Asst [name] of Reproductive Endocrinology, Department of Obstetrics and Gynecology, Inonu University Faculty of Medicine, Malatya, Turkey.

Address all correspondence to:

[name], Asst. [name] of Anesthesiology and Reanimation, Inonu University Medical Faculty, Malatya, Turkey

Mail: [contact]

[contact]

[contact]

A short title: Anesthesia Management of in Vitro Fertilization

Conflict of Interest:

The authors declare that they have no conflict of interest.

Funding Information:

None

Study Protocol

This trial was approved by the Local Ethic Committee of Inonu University (Protocol no: 2018/56, Approval Date: 18.04.2018). We conducted a prospective, randomized controlled clinical trial with 140 female patients undergoing in vitro fertilization (IVF) at an university hospital.

Patients with American Society of Anesthesiology (ASA) scores of I-II and who were aged 18–55 years old will be included in our study. Patients will be interviewed before surgery to obtain informed consent. Patients with ASA III-IV, under 18 years of age, over 55 years of age, uncontrolled diabetes mellitus, cardiovascular, pulmonary disease, cerebrovascular events, patients with an allergy to anesthetic drugs pregnant were excluded. Patients who refused informed consent will be also excluded.

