All of the patients one day before surgery; hemoglobin, hematocrit, prothrombin time, active partial thromboplastin time, aspartate aminotransferase, alanine aminotransferase will be evaluated. Electrocardiography and preoperative anesthetic evaluations will be performed. The patients who will agree to participate in the study will fill the demographic data form and STAI TX-1 (State Anxiety Scale Scale) form 2 hours before the procedure. Standard monitoring procedures will be used, including heart rate (HR), noninvasive blood pressure (NIBP), electrocardiogram (ECG), and peripheral oxygen saturation (SpO₂).

Age, gender, height, weight, body mass index (BMI), ASA scores, laboratory values, duration of anesthesia, duration of the procedure, concomitant diseases, preoperative symptoms, anesthetic drugs and doses used, causes and duration of infertility, anesthesia and complications of surgery will be recorded. HR (heart rate), SAB (systolic arterial pressure), DAB (diastolic arterial pressure), MAP (mean arterial pressure), DSS (respiratory rate), peripheral oxygen saturation (SpO₂) values will be recorded at preoperative, peroperative and postoperative

periods. Patients, who will not experience complications during the procedure, will be transferred to the post-anesthesia care unit (PACU) after the procedure. VAS score (Visuel Analog Scale) and RAMSEY sedation score will be recorded for the patients followed up in the PACU. Patients will be transferred to the service when they achieved a score of 9 or higher on the Modified Aldrete score (range 0 –12; scores of 9 and above indicate that the patient can be discharged from the PACU). In all patients, postoperative analgesia will be achieved IV analgesic medication using appropriate doses of paracetamol (1 gr, IV). Patients will complete the QoR-40 questionnaire, which is a Patient Satisfaction Survey, 24 hours after discharge.

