Randomization was performed with the MedCalc for Windows (medcalc.com.tr.), version 16 statistical software. 140 patients will be randomly allocated to two study groups: Sedation Analgesia group (Group S, $n = 70$) and Maryngeal Mask Airway, LMA (Group L, $n = 70$). Midazolam $0.05 - 0.1 \text{ mg} \cdot \text{kg}^{-1}$ IV will be performed for premedication before the procedure in both groups. No inhalation anesthetics will be used in groups. In both groups, Anesthesia will be induced and maintained with propofol $1-2 \text{ mg} \cdot \text{kg}^{-1}$ IV, remifentanil $0.05 - 0.1 \text{ mcg kg}^{-1}$ IV or fentanyl $1-2 \text{ mcg kg}^{-1}$ IV.

Statistical Analysis:

Data will be analyzed using the Statistical Package for the Social Sciences program (SPSS 22.0, IBM). As some pre and anesthetic characteristics of patients will be distributed abnormally nonparametric statistics will be used. Quantitative data are presented as mean or standard deviation and categorical data are shown as numbers or percentages. Continuous variables will be compared between the groups using Mann-Whitney U-test. Categorical variables will be summarized using frequencies and percentages (%) and compared between the groups using Chi-Squared Test. The results will be evaluated at a 95% confidence interval at a significance level of $p<0.05$.

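### Later vital signs are compared without using their recorded preoperative values, and the planned 95% confidence interval is attached to no effect estimate

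*Combined protocol and SAP*

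**What the plan says.** The Study Protocol section lists heart rate, systolic, diastolic and mean arterial pressure, respiratory rate and SpO2, and states that these "values will be recorded at preoperative, peroperative and postoperative" periods. Each of the six signs therefore has a preoperative reading and at least two later ones.

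The other scales are described at one stage only. State anxiety (STAI) is completed 2 hours before the procedure. Pain and sedation are scored afterwards: "VAS score (Visuel Analog Scale) and RAMSEY sedation score will be recorded for the patients followed up in the PACU". For satisfaction, "Patients will complete the QoR-40 questionnaire, which is a Patient Satisfaction Survey, 24 hours after discharge". The title names the outcomes of interest: "on Anxiety Level and Patient Satisfaction in Patients with in Vitro Fertilization".

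The Statistical Analysis section justifies rank methods as follows: "As some pre and anesthetic characteristics of patients will be distributed abnormally nonparametric statistics will be used". It then states "Continuous variables will be compared between the groups using Mann-Whitney U-test", with no covariate, change score or repeated-measures model. On presentation it says "Quantitative data are presented as mean or standard deviation". Its only mention of an interval is "The results will be evaluated at a 95% confidence interval", in the sentence that sets the 0.05 significance level.

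**The concern.** There are two separate issues.

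**Unused baseline.** Where a later vital sign is correlated with the same patient's preoperative value, part of its spread is predictable. An unadjusted comparison leaves that spread in the error term. A real difference between sedation and LMA is then more likely to be missed, although the data needed to sharpen the comparison are already collected.

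**No effect estimate.** A Mann-Whitney p-value does not test a difference in means. The plan shows means and SDs beside it, names no measure of the difference between groups, and does not say what its 95% interval is an interval for. This reaches QoR-40, the satisfaction measure. After a non-significant result, a reader would have no planned statement of how large a difference remains compatible with the data.

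**Working it through.** **Inputs from the documents:** 70 patients per group; significance level 0.05; six vital signs at three periods; unadjusted Mann-Whitney test. The plan gives no effect size, SD, power or correlation, so there is no figure of its own to reproduce.

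**Assumptions:** two-sided test; true shift of 0.4 SD; correlation ρ between preoperative and later value from 0 to 0.7.

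**Step 1: analytic scale.** The 95% half-width for an unadjusted mean difference is 1.96 × √(2/70) = 0.331 SD. Linear baseline adjustment multiplies the variance by 1 − ρ²:
- ρ = 0.3: factor 0.91, half-width 0.331 × √0.91 = 0.316 SD
- ρ = 0.5: factor 0.75, half-width 0.287 SD
- ρ = 0.7: factor 0.51, half-width 0.237 SD

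On normal data the Mann-Whitney test has efficiency 3/π, so 70 per group acts like 70 × 3/π = 66.8. Power at 0.4 SD is Φ(0.4/√(2/66.8) − 1.96) = Φ(0.35), or about 64%.

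**Step 2: simulated power (%).** 20,000 runs per cell. Rank ANCOVA regresses the ranked outcome on group and ranked baseline. The SpO2-like variable is min(100, round(98 + 1.5z)) at both times, with ρ on the latent scale.

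| ρ | Normal: Mann-Whitney | Normal: rank ANCOVA | SpO2-like: Mann-Whitney | SpO2-like: rank ANCOVA |
|---|---|---|---|---|
| 0 | 63.4 | 63.2 | 61.1 | 60.8 |
| 0.1 | 63.7 | 63.8 | 60.9 | 61.0 |
| 0.2 | 63.0 | 64.6 | 60.5 | 61.9 |
| 0.3 | 63.0 | 66.3 | 60.8 | 63.8 |
| 0.5 | 63.2 | 73.9 | 60.2 | 70.6 |
| 0.7 | 63.4 | 87.9 | 60.9 | 83.8 |

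Together with repeat runs, the ranges are about 60–64% unadjusted against 64–67%, 70–76% and 83–89% at ρ = 0.3, 0.5 and 0.7. Rejection under no difference was 4.7–5.2% for both tests.

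**Step 3: sensitivity.** On normal data at ρ = 0.3, 0.5 and 0.7, a 0.3 SD shift gives about 40% against 43, 50 and 65%. A 0.5 SD shift gives 81–82% against 85, 91 and 97%. On log-normal data with a 0.4 SD shift (4,000 runs), Mann-Whitney gives 82–84%, rank ANCOVA 85, 91 and 98%, and ordinary ANCOVA 69, 76 and 90%. Ordinary ANCOVA can therefore do worse than the planned test on skewed data. Rank ANCOVA did not.

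**Step 4: which effect estimate?** The usual companion to a Mann-Whitney test is the Hodges-Lehmann shift. On normal data at 70 per group its half-width is about 1.96 × √(2/70) × √(π/3) = 0.339 SD. It behaves poorly on tied whole-number scales. In simulations with Mann-Whitney significant in about 60–63% of trials, its 95% interval excluded 0 in only:
- about 3–4% of trials for SpO2-like data
- about 2–5% for an assumed whole-number, floored VAS
- about 46–49% for an assumed QoR-40 (mean 180, SD 15, capped at 200)

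The point estimate was exactly 0 in 46% of SpO2-like and 55% of VAS-like trials. It cannot be a blanket prescription here.

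**The case against.** The strongest reply is that the vital-sign point is an optional efficiency gain. The test is valid, vital signs are not in the title, and no hypothesis about them is stated. The gain also depends on a correlation, between preoperative readings and readings under or after anaesthesia, that the documents do not give. All of this stands and limits the importance. It does not remove the gain, since adjustment costs at most about 0.3 points of power when the correlation is zero.

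It is also fair that normal-data figures fit poorly with a plan that expects non-normality. On log-normal data the gain is smaller, about 3, 8 and 15 points at ρ = 0.3, 0.5 and 0.7 (85.4 − 82.5, 90.9 − 82.5, 98.2 − 83.6).

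An adjusted p-value beside an unadjusted interval is itself a mismatch. In simulated trials, rank ANCOVA and the unadjusted rank test disagreed on significance in about 8–28% at ρ = 0.3 to 0.7. That is a real cost and must be declared.

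Finally, with arm means, SDs and 70 per group a reader can derive a mean difference and a large-sample interval, so size is not wholly hidden. What remains is narrower: the plan names no effect measure for its stated interval, and the displayed summaries do not match the test. The wording on means and SDs is probably loose drafting for both together, which does not change this.

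**Conclusion.** The point holds as an improvement worth making. For later vital signs the plan gives up precision it already has: about 3 points of power at a correlation of 0.3, 10–11 at 0.5 and 23–25 at 0.7 on normal or SpO2-like data, and 0–2 points at 0.2 or below. These figures rest on the assumed 0.4 SD shift, correlations and distributions. The missing effect estimate is a smaller fault, but it reaches QoR-40.

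Three stronger readings do not follow:
- A reader might infer that the unadjusted test is biased. Randomisation protects it, and simulated error stayed near 5%.
- A reader might infer that the title outcomes lose power in the same way. STAI is described only before the procedure and QoR-40 only after discharge, so neither has a baseline and follow-up pair.
- A reader might fault the plan for not adjusting QoR-40 for preoperative STAI. That is optional, and its absence is not an error.

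**What to change.** **Vital signs.** For each peroperative and postoperative sign, prespecify ANCOVA on ranks with group and the ranked preoperative value of the same sign, and no data-dependent switch of model. State which preoperative reading is the covariate (one taken before premedication) and which later reading is the outcome; the Study Protocol section settles neither. Six signs at two later periods give at least 12 tests, so label these p-values exploratory.

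**Effect estimates.** For QoR-40, VAS and other continuous outcomes, keep the Mann-Whitney test where no baseline exists and report two quantities beside the p-value:
- the probability of superiority, U/(n₁n₂) with ties counted as half, with a tie-corrected 95% interval; this is the quantity closest to the test
- the mean difference in original units with a Welch or bootstrap 95% interval, as a description of size

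Do not require the Hodges-Lehmann interval for every outcome.

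**Declaration.** Say that the vital-sign p-value comes from the rank ANCOVA, that the accompanying interval is unadjusted, and that the two can disagree.

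**Cost.** A few sentences in the SAP and some extra analyses of measurements already planned. No additional patients or assessments.
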